Rumah Sakit Ibu & Anak
STELLA MARIS
Women's & Children's Hospital
KLINIK BAYI TABUNG HALIM FERTILITY CENTER
[name]
Telp : [name], [contact]

Efficacy of Platelet-Rich Plasma on Blastocyst Formation in ICSI Cycles Involving Low-Quality Sperm: A Randomized Study

Protocol Version:

Version 1.0

Document Date:

November 17, 2022

Sponsor / Study Site:

Halim Fertility Center, Stella Maris Women's and Children's Hospital, Medan, Indonesia

Ethics Approval Number:

608.1/Dir/RSIA.SM/XII/2022

Principal Investigator:

[name]

Rumah Sakit Ibu & Anak
STELLA MARIS
Women's & Children's Hospital
KLINIK BAYI TABUNG HALIM FERTILITY CENTER
[name]
Telp : [name], [contact]

Study Protocol and Statistical Analysis Plan

Efficacy of Platelet-Rich Plasma on Blastocyst Formation in ICSI Cycles Involving Low-Quality Sperm: A Randomized Study

1. Background and Rationale

Platelet-rich plasma (PRP) is an autologous concentration of platelets containing growth factors that promote tissue regeneration and reduce oxidative stress. Poor sperm quality, particularly in severe oligoasthenoteratozoospermia (SOAT), is associated with impaired fertilisation, reduced embryo development, and lower blastocyst formation rates in intracytoplasmic sperm injection (ICSI) cycles.

Previous findings suggest that PRP improves sperm motility, morphology, and DNA integrity. However, its effect on downstream embryological outcomes remains insufficiently explored. This study aims to evaluate whether PRP incubation prior to ICSI improves blastocyst formation and embryo quality.

2. Objectives

Primary Objective:

To evaluate the effect of PRP incubation on blastocyst formation rate in ICSI cycles involving low-quality sperm

Secondary Objectives:

- To assess fertilisation rate
- To assess cleavage rate
- To evaluate blastocyst quality (good, fair, poor)

3. Study Design

This study is a prospective, randomized controlled study conducted at Halim Fertility Center, Stella Maris Women's and Children's Hospital, Medan, Indonesia, between January 2023 and August 2023.

Participants were recruited using consecutive sampling. Couples undergoing more than one IVF-ICSI cycle were excluded.

4. Participants

4.1 Inclusion Criteria (Male)

- Sperm concentration <5 million/mL
- Total motility <42%
- Normal morphology <4%
- Provided informed consent

4.2 Exclusion Criteria (Male)

- Leukospermia
- Reproductive infections (HIV, hepatitis)
- Recent drug exposure (within 3 months)
- Fever within 3 months
- Testicular carcinoma
- Use of second ejaculate or cryopreserved sperm
- Retrograde ejaculation
- Coagulopathy

4.3 Exclusion Criteria (Female)

- Age ≥ 40 years
- Polycystic ovarian syndrome (Rotterdam criteria)
- Low ovarian reserve (AFC <5 or AMH <0.5–1.1 ng/mL)

5. Randomisation and Blinding

Participants were randomly allocated into two groups using registration number parity:

Odd numbers: PRP group

Even numbers: Control group

Embryologists performing ICSI and outcome assessments were blinded to group allocation.

6. Interventions

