6.1 PRP Group

Sperm samples were incubated with autologous PRP for one hour prior to ICSI. PRP was prepared from 10 mL peripheral blood using a two-step centrifugation process. A ratio of 30 μ L PRP to 0.3 mL sperm (10% v/v) was used.

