6.2 Control Group

Standard sperm preparation without PRP incubation.

All samples underwent density gradient centrifugation prior to intervention.

7. Ovarian Stimulation and ICSI Procedure

Female partners underwent controlled ovarian stimulation using a GnRH antagonist protocol. Oocyte retrieval was performed 35–36 hours after hCG trigger. Mature oocytes (MII) were inseminated using ICSI 38–42 hours post-trigger.

8. Embryo Culture and Assessment

Fertilisation assessed at 17 ± 1 hours (2PN). Cleavage assessed on day 3. Blastocyst assessed on day 5.

Blastocysts were graded using the Gardner classification:

Good: AA

Fair: AB, BA, BB

Poor: AC, CA, BC, CB, CC

All assessments were performed by a single blinded embryologist.

9. Outcome Measures

Primary Outcome:

Blastocyst formation rate

Secondary Outcomes:

Fertilisation rate

Cleavage rate

Blastocyst quality

10. Statistical Analysis Plan

Statistical analysis was conducted using SPSS version 21.0 (IBM Corp., Armonk, NY, USA).

Normality assessed using Shapiro–Wilk test

Continuous variables analysed using Student's t-test or Mann–Whitney U test

Categorical variables analysed using Chi-squared test

Data presented as mean \pm standard deviation (SD) or median (IQR)

Categorical data presented as percentages (%)

Statistical significance set at $P < 0.05$

No adjustment for multiple comparisons was performed as outcomes were pre-specified.

Rumah Sakit Ibu & Anak
STELLA MARIS
Women's & Children's Hospital
KLINIK BAYI TABUNG HALIM FERTILITY CENTER
[name]
Telp : [name], [contact]

11. Ethical Considerations

The study was approved by the Institutional Ethics Committee of Stella Maris Women's and Children's Hospital (Approval No. 608.1/Dir/RSIA.SM/XII/2022; approved on 19 December 2022).

Written informed consent was obtained from all participants prior to enrolment.

12. Data Confidentiality

All participant data were anonymized and handled in accordance with ethical and regulatory standards. No identifiable personal data are included in this document.

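### The arm can be read from the registration number, apparently before stimulation and retrieval, yet PRP is used only after retrieval and no rule covers couples lost before ICSI

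*Combined protocol and SAP*

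**What the plan says.** All references are to the combined protocol and SAP.

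- **Allocation (Section 5).** "Participants were randomly allocated into two groups using registration number parity", with "Odd numbers: PRP group" and "Even numbers: Control group". The kind of number, its date of issue and the moment of disclosure are not given. No separate allocation event is described.
- **Masking (Section 5).** "Embryologists performing ICSI and outcome assessments were blinded to group allocation". Section 8 adds a single blinded assessor. The couple, the registration staff and the clinicians responsible for stimulation and retrieval are not mentioned.
- **Care before the compared step (Section 7).** "Female partners underwent controlled ovarian stimulation using a GnRH antagonist protocol". Then "Oocyte retrieval was performed 35–36 hours after hCG trigger" and "Mature oocytes (MII) were inseminated using ICSI 38–42 hours post-trigger".
- **The compared step (Section 6.1).** "Sperm samples were incubated with autologous PRP for one hour prior to ICSI". Section 6.2 gives control samples standard preparation and puts density gradient centrifugation ahead of the intervention in both arms.
- **Exits before ICSI.** Section 4.2 excludes second-ejaculate and cryopreserved samples, which may be known only when the sample is produced. Section 7 injects mature oocytes only.
- **Analysis (Sections 9 and 10).** There is no analysis population, no denominator for the blastocyst rate, no missing-data rule and no rule for allocated couples who do not reach ICSI.

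**The concern.** The arms are meant to differ in one laboratory step on the day of ICSI. Under a parity rule, anyone who sees the number knows the arm. If the number is issued at clinic or study registration, that knowledge is available during stimulation, trigger, retrieval and sample production, all of which come before PRP is used.

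Two routes to bias follow. First, care that shapes the oocytes could differ by arm. Second, couples could leave at different rates by arm, through a cancelled cycle, no mature oocyte or no usable fresh sample. Either difference would appear in the blastocyst comparison as an effect of PRP.

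This is separate from the weakness that parity lets staff foresee the arm at enrolment. A concealed random list opened at registration would cure that weakness, but would still leave the arm known during earlier care and would leave loss after allocation untouched.

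**Working it through.** **1. When treatment starts relative to retrieval.** Inputs are from Sections 6.1 and 7: retrieval at 35–36 h after trigger, ICSI at 38–42 h, incubation for 1 h before ICSI.

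- Start of incubation = ICSI time − 1 h: 38 − 1 = 37 h to 42 − 1 = 41 h.
- Shortest gap after retrieval: 37 − 36 = 1 h. Longest: 41 − 35 = 6 h.

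The plan's own times therefore place PRP after retrieval.

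**2. When the arm can be known.** Section 5 makes the arm a function of the number alone, so it is readable from issue. The date of issue is missing. Section 11 places consent before enrolment but does not tie either to the number or to stimulation. Issue before stimulation is the natural reading, because nothing in Sections 6 to 8 describes an allocation on the day of ICSI. It remains an inference.

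**3. Size of a loss bias.** The plan gives no sample size, expected rate, SD or dropout, so there is no figure of its own to reproduce. Every input from here on is an assumption.

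Let d be the fraction of an arm lost before ICSI, and δ the amount by which the lost couples' blastocyst rate falls below the mean of the whole arm (same δ in both arms). The retained mean exceeds the whole-arm mean by δ·d/(1 − d). With no PRP effect:

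bias = δ × [d_PRP/(1 − d_PRP) − d_control/(1 − d_control)]

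| Loss, PRP vs control | Bracket | δ = 10 points | δ = 20 points |
|---|---|---|---|
| 5% vs 5% | 0 | 0 | 0 |
| 10% vs 5% | 0.1111 − 0.0526 = 0.0585 | 0.58 | 1.17 |
| 20% vs 10% | 0.2500 − 0.1111 = 0.1389 | 1.39 | 2.78 |
| 20% vs 5% | 0.2500 − 0.0526 = 0.1974 | 1.97 | 3.95 |

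Swapping the arms reverses the sign, so the bias could run for or against PRP.

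A direct example agrees with the third row. Suppose 20% of couples have a 20% rate and 80% have 45%, so the mean is 0.8 × 0.45 + 0.2 × 0.20 = 0.40. If all the poor-prognosis couples leave the PRP arm but only half leave control, the retained means are 0.45 and (0.36 + 0.02)/0.90 = 0.422, a spurious 2.8 points.

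**4. Effect on the type I error.** Use a two-sided 5% test, normal approximation, SE = SD × √(2/n), SD 25–30 points and n = 50–100 couples per arm (assumed). The error is Φ(b/SE − 1.96) + Φ(−b/SE − 1.96).

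- Bias b = 0.58: SD 30, n = 50 gives SE = 6.0 and an error of 5.1%; SD 25, n = 100 gives SE = 3.54 and 5.3%.
- Bias b = 3.95: the same two settings give 10.1% and 20.1%.

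**The case against.** The strongest reply is that the premise about timing is not in the document. The number could be a laboratory or study number issued late. The exclusion of second-ejaculate and cryopreserved samples is even compatible with enrolment on the day of ICSI. This stands: a reader might infer that the arm was certainly fixed before stimulation, and the text does not support that as fact.

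Likewise, a reader might infer that clinicians and couples were unmasked and acted on it. Section 5 is only silent about them. No reason is given why a sperm-laboratory step would change stimulation, and no loss or imbalance is recorded.

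The illustration can also be called harsh. The 2.8-point example needs every poor-prognosis couple to leave one arm and half to leave the other. Section 4.3 already excludes low ovarian reserve and women aged 40 or over, which plausibly limits cancelled cycles and cycles without a mature oocyte. With 10% against 5% loss the bias is 0.6–1.2 points, and at 0.58 points the type I error barely moves.

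It can be said too that lost couples are recoverable by counting them as zero. That depends on a denominator the plan does not define, and it would not remove differences in earlier care.

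Finally, changing only the day of allocation achieves nothing while parity still reveals the arm. That is correct, and the fix has to replace parity as well.

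What the reply leaves untouched is that the arm is readable from the number, PRP follows retrieval, masking is described for embryologists only, and loss before ICSI has no rule.

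**Conclusion.** The concern holds as a gap in protection. The plan does not prevent earlier care or loss before ICSI from differing by arm, and the comparison would absorb any such difference. That the arm precedes stimulation is the likely reading, not an established one.

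The document does not support saying that a bias occurred, nor treating any figure above as an estimate of it. The range of about 0.6 to 4 points rests on assumed losses of 10–20% against 5% and on lost couples being 10–20 points worse. With equal and comparable loss it is zero. The point deserves a change because a better rule is available at little cost, not because harm has been shown.

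**What to change.** Amend Section 5 as follows.

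1. Replace parity with a concealed computer-generated list.
2. Have it opened by a laboratory person who takes no part in ICSI or grading, so that the stated blinding of embryologists is kept.
3. Open it on the day of retrieval, after both partners' eligibility, at least one mature oocyte and a prepared fresh sample are confirmed, and immediately before the PRP or control step. Consent stays before enrolment, as in Section 11.
4. Analyse all couples so allocated, in the arm allocated, and state the denominator of the blastocyst rate. A rate per mature oocyte would be defined for each of them.

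Care and loss up to that point would then be independent of the arm. No additional blood draw from control men is needed.

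The cost is protocol wording and same-day logistics. With retrieval at 36 h and ICSI at 38 h, only 38 − 1 − 36 = 1 h remains before the one-hour incubation. The stated ICSI window runs to 42 h, which eases this. The plan gives no duration for PRP preparation, so the sponsor should confirm that the sequence fits its own times.

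The document is written in the past tense and gives a study period of January to August 2023, so recruitment may be complete. In that case, report when registration numbers were issued, who knew the arm before ICSI, and losses with reasons by arm from registration to ICSI.

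### Allocation by odd or even registration number is a deterministic, quasi-random rule with no described concealment, so the plan does not support calling the study randomised

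*Combined protocol and SAP*

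**What the plan says.** Section 3 gives the design label: "This study is a prospective, randomized controlled study". The title makes the same claim. Section 3 also says "Participants were recruited using consecutive sampling".

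Section 5 gives the whole allocation method: "Participants were randomly allocated into two groups using registration number parity". The rule is "Odd numbers: PRP group" and "Even numbers: Control group". No sequence generator, blocking, stratification, concealment or independent holder of assignments appears in Section 5 or elsewhere.

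Blinding is stated twice. Section 5 says "Embryologists performing ICSI and outcome assessments were blinded to group allocation", and Section 8 says "All assessments were performed by a single blinded embryologist". Staff who register, screen or recruit couples are not mentioned.

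Section 11 places written consent before enrolment. The document does not say where the issue of the registration number falls relative to screening, consent or enrolment.

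**The concern.** Randomisation serves two purposes. It makes the arms comparable apart from chance, and, when concealed, it prevents anyone from choosing who enters which arm. A parity rule applied to an administrative number does neither by construction. The arm is a fixed function of a number that clinic staff issue and can read.

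The plan leaves some openings for an arm-dependent decision:

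- The AMH limit in Section 4.3 is written as a range, and the fever and drug-exposure exclusions in Section 4.2 may rest on history. These leave room for judgement.
- Section 6.1 takes 10 mL of blood for PRP, while Section 6.2 describes no draw for controls. If the arm is known, willingness to take part could differ by arm.
- Section 10 lists only unadjusted two-group tests, so the planned analysis would not correct an imbalance.

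At stake is the reading of the primary comparison. Without randomisation, the P value for blastocyst formation rests on an unverified assumption that parity is unrelated to prognosis.

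**Working it through.** The plan states no sample size, power or target effect, so there is no figure to reproduce. The first step below is textual. The other three are illustrations, and their inputs are assumptions except where noted.

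**1. Label against method.** Sections 3 and 5 claim random allocation. The only mechanism given in Section 5 is odd to PRP and even to control. Given the number, the arm is determined. The label and the method do not agree, and this needs no assumption about anyone's conduct.

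**2. Predictability of the next arm.**

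| Scheme | Chance of a correct guess |
|---|---|
| Parity, number or next number visible | 100% |
| Simple random sequence, concealed | 50% |
| Permuted blocks of 4, all past allocations known | about 71% |
| Permuted blocks of 6, all past allocations known | about 68% |

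The first two follow from the definitions. The block figures come from simulating a recruiter who always guesses the arm that is currently behind. They show why block sizes should vary and past allocations should stay hidden.

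**3. False gain from steering.** Assumed: arms equal before steering; poor-prognosis share 0.30 in each; blastocyst rate 0.15 for those couples and 0.35 for the rest; no PRP effect; a fraction *d* of poor-prognosis couples steered away from PRP. An arm's rate is 0.35 − 0.20 × (its poor-prognosis share). Without steering this is 0.35 − 0.20 × 0.30 = 0.290.

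- PRP share after steering: 0.30(1 − d)/(1 − 0.30d). For d = 0.3, 0.21/0.91 = 0.231, rate 0.3038. For d = 0.5, 0.15/0.85 = 0.176, rate 0.3147.
- If those couples leave the study, control stays at 0.290. The false gain is 0.3038 − 0.2900 = 1.4 points, or 0.3147 − 0.2900 = 2.5 points.
- If they enter control instead, its share is 0.30(1 + d)/(1 + 0.30d). For d = 0.3, 0.39/1.09 = 0.358, rate 0.2784, false gain 2.5 points. For d = 0.5, 0.45/1.15 = 0.391, rate 0.2717, false gain 4.3 points.
- For d = 0 the false gain is zero in both cases.

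**4. Effect on type I error.** Section 10 sets significance at 0.05 without stating sidedness; two-sided is assumed. Also assumed: a mean prognostic difference of *s* SD between arms, *n* per arm, no treatment effect and an unadjusted z-test. With m = s/√(2/n), the error is 1 − Φ(1.96 − m) + Φ(−1.96 − m). For n = 50 and s = 0.2, √(2/50) = 0.2, so m = 1.0 and the error is 1 − Φ(0.96) + Φ(−2.96) = 17.0%.

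| Shift s | n = 30 | n = 50 | n = 100 |
|---|---|---|---|
| 0 | 5.0% | 5.0% | 5.0% |
| 0.1 SD | 6.7% | 7.9% | 10.9% |
| 0.2 SD | 12.1% | 17.0% | 29.3% |
| 0.3 SD | 21.3% | 32.3% | 56.4% |

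For a fixed shift, the error grows with sample size, so recruiting more couples would not cure it.

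**The case against.** The strongest reply is that the room for manipulation is small. Sampling was consecutive, couples with more than one cycle were excluded, and most eligibility criteria are measured thresholds or diagnoses. If numbers were issued at enrolment, consent came before the number was known. The embryologists who produced and graded the outcome are stated to be blinded.

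Much of this stands as mitigation. Consecutive sampling narrows the scope for selective enrolment, and steering 30% to 50% of poor-prognosis couples would be hard to square with it. It does not close the gap: eligibility judgement, consent and the timing of registration remain open, and the next number in a sequence may be foreseeable even when it has not yet been issued. Embryologist blinding guards against differential handling and assessment, not against selection into the arms.

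A reader might infer that staff knew the arm before consent and eligibility were settled. The document does not support that as fact, because it gives no timing for the number. A reader might also infer that embryologist blinding failed. Parity would reveal the arm to any embryologist who saw the registration number, but nothing says what identifier appeared on samples or records. Both points are open questions for the sponsor to answer.

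**Conclusion.** The point holds as a mismatch between label and method, with undescribed concealment. The method in Section 5 is quasi-random, and the terms used in the title, Section 3 and Section 5 claim more than it delivers. That conclusion rests on the text alone.

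The consequence is exposure to selection bias. It would be wrong to conclude that bias occurred or that the result is false; the plan contains no evidence of either. Certain prediction of the arm is conditional on the number, or the next one, being visible before the decision to enrol. The 1.4 to 4.3 points and the inflated error rates depend wholly on assumed inputs. With no planned effect or sample size to set them against, they show direction and mechanism rather than the likely size of bias in this study.

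**What to change.** **If couples were already allocated by parity.** This seems likely: the text is in the past tense and gives January to August 2023 as the study period, although the version is dated November 2022.

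- Change the title, Section 3 and Section 5 to *quasi-randomised (allocation by registration number)*, and limit the conclusion accordingly.
- State when and by whom numbers were issued, and which identifier the embryologists saw.
- Report the numbers screened, excluded and allocated, and the baseline characteristics, by arm.
- Add a sensitivity analysis of blastocyst formation adjusted for baseline prognostic factors already collected, for example female age, ovarian reserve and sperm parameters. It can address measured imbalance only.

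**If allocation is still open.**

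- Replace parity with a computer-generated permuted-block list with varying block sizes, held by existing staff who take no part in recruitment or embryology.
- Conceal each assignment until consent and eligibility are confirmed.
- Label samples with a code unrelated to arm.

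**Cost.** For a completed study: a less favourable design label and a small amount of extra reporting and analysis. For an open one: an amendment and a one-off list. No extra patients in either case.

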6.1 PRP Group

Sperm samples were incubated with autologous PRP for one hour prior to ICSI. PRP was prepared from 10 mL peripheral blood using a two-step centrifugation process. A ratio of 30 μ L PRP to 0.3 mL sperm (10% v/v) was used.

6.2 Control Group

Standard sperm preparation without PRP incubation.

All samples underwent density gradient centrifugation prior to intervention.

7. Ovarian Stimulation and ICSI Procedure

Female partners underwent controlled ovarian stimulation using a GnRH antagonist protocol. Oocyte retrieval was performed 35–36 hours after hCG trigger. Mature oocytes (MII) were inseminated using ICSI 38–42 hours post-trigger.

8. Embryo Culture and Assessment

Fertilisation assessed at 17 ± 1 hours (2PN). Cleavage assessed on day 3. Blastocyst assessed on day 5.

Blastocysts were graded using the Gardner classification:

Good: AA

Fair: AB, BA, BB

Poor: AC, CA, BC, CB, CC

All assessments were performed by a single blinded embryologist.

9. Outcome Measures

Primary Outcome:

Blastocyst formation rate

Secondary Outcomes:

Fertilisation rate

Cleavage rate

Blastocyst quality

10. Statistical Analysis Plan

Statistical analysis was conducted using SPSS version 21.0 (IBM Corp., Armonk, NY, USA).

Normality assessed using Shapiro–Wilk test

Continuous variables analysed using Student's t-test or Mann–Whitney U test

Categorical variables analysed using Chi-squared test

Data presented as mean \pm standard deviation (SD) or median (IQR)

Categorical data presented as percentages (%)

Statistical significance set at $P < 0.05$

No adjustment for multiple comparisons was performed as outcomes were pre-specified.

Rumah Sakit Ibu & Anak
STELLA MARIS
Women's & Children's Hospital
KLINIK BAYI TABUNG HALIM FERTILITY CENTER
[name]
Telp : [name], [contact]

11. Ethical Considerations

The study was approved by the Institutional Ethics Committee of Stella Maris Women's and Children's Hospital (Approval No. 608.1/Dir/RSIA.SM/XII/2022; approved on 19 December 2022).

Written informed consent was obtained from all participants prior to enrolment.

12. Data Confidentiality

All participant data were anonymized and handled in accordance with ethical and regulatory standards. No identifiable personal data are included in this document.

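### Blastocyst quality is compared only among embryos that became blastocysts, the event PRP is meant to change; compare good-quality blastocysts per MII oocyte injected instead

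*Combined protocol and SAP*

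**What the plan says.** All references are to the combined protocol and SAP.

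- Section 2 sets the primary objective: "To evaluate the effect of PRP incubation on blastocyst formation rate in ICSI cycles involving low-quality sperm". Blastocyst quality, in three levels (good, fair, poor), is a secondary objective there and a secondary outcome in section 9.
- Section 8: "Blastocysts were graded using the Gardner classification". Good is AA; fair is AB, BA or BB; the lowest level is "Poor: AC, CA, BC, CB, CC". An embryo that does not reach blastocyst gets no grade.
- Section 10 gives general rules and does not match outcomes to tests. For categorical data: "Categorical variables analysed using Chi-squared test". The rank test appears only under another rule: "Continuous variables analysed using Student's t-test or Mann–Whitney U test". Categorical data are shown as percentages. No multiplicity adjustment is made, on the ground that the outcomes were set in advance.
- No section states the denominator or unit of analysis for quality, and none plans a quality analysis over all injected oocytes.

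**The concern.** A grade exists only after an embryo has become a blastocyst. That happens after allocation, and the trial is run to learn whether PRP makes it happen more often. If PRP works, the PRP arm's graded set includes embryos whose counterparts in the control arm arrested and were never graded. The two graded sets are then not like with like, even with perfect allocation and blinding.

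The risk is greatest when the primary result is positive. If the additional blastocysts are mostly low grade, the report could say that PRP raises blastocyst formation but worsens quality, although no embryo that would have been good was made worse. With no multiplicity adjustment and no companion figure on a common denominator, nothing in the plan warns the reader against taking that P value at face value.

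**Working it through.** The documents state no sample size, power, effect size, grade distribution or number of oocytes per couple, so there is no planned figure to reproduce. All counts below are assumptions, and embryos are treated as independent.

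**1. Effect of the denominator, small case.** Per 100 oocytes, control has 30 blastocysts, 8 of them good. PRP yields the same 30 plus 6 poor ones.
- Among blastocysts: 8/30 = 26.7% v 8/36 = 22.2% good.
- Per oocyte: 8/100 = 8% in both arms.
- Test of good v not good: pooled 16/66 = 0.242; SE = √[0.242 × 0.758 × (1/30 + 1/36)] = 0.106; z = 0.044/0.106 = 0.42; P about 0.67.

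**2. Larger case.** Per 100 oocytes, control has 40 blastocysts graded 8/16/16 (good/fair/poor). PRP adds 10, all poor, giving 8/16/26 of 50.
- Good: 8/40 = 20% v 8/50 = 16%. Poor: 16/40 = 40% v 26/50 = 52%.
- Good per oocyte: 8% in both arms.
- With 5 or 15 extra instead of 10, PRP good is 8/45 = 18% or 8/55 = 15%, and PRP poor is 21/45 = 47% or 31/55 = 56%.

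**3. How often chi-squared would reject in case 2.** The noncentrality is λ = Σ n₁(p−m)²/m + Σ n₂(q−m)²/m, where p = (0.20, 0.40, 0.40), q = (0.16, 0.32, 0.52) and pooled m = (16, 32, 42)/90. At 100 oocytes per arm, n₁ = 40 and n₂ = 50, so λ = 0.71 + 0.57 = 1.29. It grows in proportion to the number of oocytes. Power comes from the noncentral chi-squared distribution with 2 df at the 5% level.

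| Oocytes per arm | λ | Chi-squared rejects | 1-df trend test rejects |
|---|---|---|---|
| 100 | 1.29 | 16% | 17% |
| 200 | 2.57 | 28% | 30% |
| 300 | 3.86 | 40% | 41% |

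Simulating the chi-squared column gave 16%, 28% and 41%. The expected proportions point to worse quality with PRP. The trend test rejects about as often, so using the order of the grades does not remove the problem. A comparison of good blastocysts per oocyte has a true difference of zero in this case.

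**4. Does ignoring the order cost power?** This is a separate question. With 100 graded blastocysts per arm:
- 20/40/40 v 30/43/27 (a nearly uniform shift): chi-squared 47%, rank test 57%. For a proportional-odds shift the noncentralities needed for 80% power are 9.63 (2 df) and 7.85 (1 df), and 9.63/7.85 = 1.23, or about 23% more blastocysts.
- 20/40/40 v 30/20/50 (a non-monotone change): chi-squared 81%, trend or rank test 5% to 6%. With scores 2/1/0 the means are equal (0.4 + 0.4 = 0.8 and 0.6 + 0.2 = 0.8), so a trend test has nothing to detect.

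**The case against.** **The test is inferred.** Section 10 never assigns chi-squared to blastocyst quality. If quality were summarised per couple as a percentage in each grade, the t-test or Mann–Whitney rule could apply. This stands: chi-squared is the likeliest reading, not a stated fact. The selection remains either way, because a per-couple percentage among blastocysts uses the same graded set.

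**The harm is hypothetical.** Nothing in the documents says that extra blastocysts would be poor, and the small case is far from significant. This also stands. The higher rejection rates need 10 extra per 100, all poor. The formation rate will be reported alongside, so a careful reader could see that more blastocysts formed. That softens the problem, but leaves the reader to rebuild a comparison the plan could simply provide.

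**Chi-squared is wrong for ordered grades.** A reader might infer this. The documents do not support it: Pearson chi-squared is a valid test of a 2×3 table, the percentages by arm show direction, and the power loss arises only for a monotone shift that the documents give no reason to assume.

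**A four-level ordered model is needed, with no blastocyst as the lowest level.** A reader might infer this too. Such a model absorbs the primary outcome, so it can be positive merely because more blastocysts form. In the small case its proportional-odds assumption also fails: the odds ratio for any blastocyst is (36/64)/(30/70) = 1.31, but for good v the rest it is (8/92)/(8/92) = 1.00.

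**Conclusion.** The concern holds in this form: quality is graded only in embryos selected by the primary outcome, and the plan has no quality comparison on all injected oocytes. The comparison misleads only to the extent that PRP changes which embryos reach blastocyst, which is the trial's own hypothesis. Under the assumed cases the percentage good falls by about 4 points (27% to 22%, or 20% to 16%) with no change in good blastocysts per oocyte. The chance of a significant result ranges from 16% to 41% at 100 to 300 oocytes per arm when 10 poor blastocysts per 100 are added. These sizes rest on invented counts and on independent embryos; the direction of the problem does not.

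The documents do not support concluding that the quality analysis is invalid, that PRP will appear harmful, or that a particular ordinal model is required. The primary analysis is untouched. This is an inexpensive improvement to one of three secondary outcomes.

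**What to change.** In section 10, define the quality comparison as good-quality (AA) blastocysts per MII oocyte injected, by arm, with a 95% CI that allows for several oocytes per couple, for example by logistic GEE or cluster-robust standard errors. The treatment acts on sperm, so it should not alter how many mature oocytes a couple has, and the denominator is free of the selection. Report the good/fair/poor split among blastocysts, with counts, as descriptive only.

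The cost is SAP wording; the data needed are those the protocol already generates. The downside is that the measure combines formation and quality, so it should be read beside the blastocyst formation rate and the per-grade counts. An ordered test of the grades may be added as a sensitivity analysis, on the understanding that it gains power only for a monotone shift and does not cure the selection. Section 10 is written in the past tense; if outcome data have already been examined, label the new comparison post hoc and report it all the same.
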